8.3 ADVERSE EVENT REPORTING REQUIREMENTS

8.3.1 ROUTINE ADVERSE EVENT REPORTING

All Adverse Events **must** be reported in routine study data submissions. **AEs reported using the Serious Event Reporting Form and/or MedWatch Form discussed below must also be reported in routine study data submissions.**

8.3.2 SERIOUS ADVERSE EVENT REPORTING TO THE COORDINATING CENTER

All serious adverse events (as defined in section 8.2.3.1) and all adverse events that have been specified to require expedited reporting in the section 8.2.3.2 occurring on this study require expedited reporting to the University of Chicago Comprehensive Cancer Center (UC CCC). The responsible Research Nurse or other designated individual at the treating site should report the SAE to the Principal Investigator and the CCTO by the end of the business day when s/he becomes aware of the event. Events occurring after business hours should be reported to the CCTO by 12pm (noon) the next business day. Reports should be made using the ‘Serious Event Report’ Form.

All unexpected adverse reactions must be reported to the IND holder so that the University of Chicago CCTO can inform the FDA. The responsible Research Nurse or other designated individual at the treating site should provide a complete written report using the FDA MedWatch 3500A form. The completed form should be sent to the CCTO at [contact] within the specified timelines below regardless of whether all information regarding the event is available. If applicable, a follow-up report should be provided to the CCTO if additional information on the event becomes available.

Study staff should not forward any adverse event reports directly to the FDA. The CCTO will report all events to the FDA as per the current FDA guidelines.

Fatal or Life-threatening Events: within 4 calendar days from treating investigator knowledge of the event

All Other Reportable Events: within 10 calendar days of treating investigator knowledge of the event

All serious adverse events should also be reported to the local IRB of record according to their policies and procedures.

8.4 TRIAL GOVERNANCE AND OVERSIGHT

8.4.1 DATA MONITORING COMMITTEE

The principal investigator will ensure that trial is conducted and data are generated,

documented, and reported in compliance with the protocol, accepted standards of Good Clinical Practice, and all applicable federal, state, and local laws, rules and regulations relating to the conduct of the clinical trial. The trial will specifically be evaluated by the principal investigator after the first 12 patients are enrolled to assess if the trial should be continued.

A quality assurance audit/inspection of this study may be conducted by regulatory authorities. The quality assurance auditor will have access to all medical records, the investigator's study-related files and correspondence, and the informed consent documentation of this clinical study.

9.0 STATISTICAL ANALYSIS PLAN

9.1 STATISTICAL ANALYSIS PLAN SUMMARY

This section contains a brief summary of the statistical analysis for this trial. Full details can be found in the statistical analysis plan (SAP) in Section 8.2.

9.1.1 SAFETY ANALYSES

The study will initially enroll 12 patients in the first stage of the two-stage trial design. The accrual rate will be 1 patient/month in relapsed/refractory myeloid and B cell malignancies following allogeneic stem cell transplant to assess the safety and feasibility of pembrolizumab. If at least 5 of the first 12 patients complete pembrolizumab treatment without developing a DLT, we will open an expansion cohort to enroll with plans to enroll 14 additional patients should DLT-associated stopping rule not be met in the first 12 patients. Specifically, if 5 or more of the first 12 enrolled patients develop a DLT, including grade 3-4 GHVD, then the study will be halted. If at least 14 of the 26 patients remain DLT-free, we would have sufficient evidence to warrant further study of pembrolizumab in a future trial. Furthermore, if severe GVHD (grade 3-4) develops within the first 90 days of pembrolizumab treatment in each of the first 5 patients treated on the study (i.e. develop a DLT), it will be permanently closed to accrual as a measure to ensure safety.

Toxicity will be graded per the CTCAE guidelines and the maximally tolerated dose will be defined a less or equal than 1 in 6 patients with DLTs. All patients who receive any amount of the study drug will be evaluable for toxicity.

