8.2 ASSESSING AND RECORDING ADVERSE EVENTS

The rate of subject entry and expansion will depend upon assessment of the safety profile of patients entered at the previous dose level. Toxicity will be evaluated according to the NCI Common Terminology Criteria for Adverse Events (CTCAE), Version 4.0 (see Appendix E). If at least 5 of the first 12 patients complete pembrolizumab treatment without developing a DLT, we will open an expansion cohort to enroll with plans to enroll 14 additional patients should DLT-associated stopping rule not be met in the first 12 patients. If at least 14 of the 26 patients remain DLT-free, we would have sufficient

evidence to warrant further study of pembrolizumab in a future trial.

This particular safety stopping rule is based on the expected 50% rate of GVHD that has been reported to develop after DLI therapy³⁰. The inclusion of an expansion cohort will enable a further and more robust safety signal, as well as provide a larger cohort of patients in whom to assess clinical response, especially given the mixture of diseases that are being included in this study.

8.2.1 DEFINITION OF AN OVERDOSE FOR THIS PROTOCOL AND REPORTING OF OVERDOSE TO THE SPONSOR

For purposes of this trial, an overdose will be defined as any dose exceeding the prescribed dose for pembrolizumab will be defined as any dose of 1000 mg or greater. No specific information is available on the treatment of overdose of pembrolizumab. In the event of overdose, pembrolizumab should be discontinued and the subject should be observed closely for signs of toxicity. Appropriate supportive treatment should be provided if clinically indicated.

If an adverse event(s) is associated with (“results from”) the overdose of pembrolizumab, the adverse event(s) is reported as a serious adverse event, even if no other seriousness criteria are met.

If a dose of pembrolizumab according to the definition of overdose is administered without any associated clinical symptoms or abnormal laboratory results, the overdose is reported as a non-serious Event of Clinical Interest (ECI), using the terminology “accidental or intentional overdose without adverse effect.”

All reports of overdose with and without an adverse event must be reported within 24 hours to the sponsor either by electronic media or paper.

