9.1.3 INTERIM ANALYSIS

After the first 12 patients have been enrolled and have received at least 1 dose of pembrolizumab, an interim safety analysis will be performed. If < 5 of the first 12 patients develop a DLT (including grade 3-4 acute GVHD) following pembrolizumab treatment, an expansion cohort of 14 additional patients will be enrolled in order to obtain a more robust safety signal, as well as to enhance numbers of treated patients for efficacy analyses, given that patients with a wide variety of hematological malignancies will be enrolled. However, if ≥ 5 of the first 12 enrolled patients develop a DLT, then the study will be permanently closed to accrual. Furthermore, if severe GVHD (grade 3-4) develops in each of the first 5 patients treated on the study, it will be permanently closed to accrual as a measure to ensure safety.

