9.2.4 STATISTICAL METHODS

9.2.4.1 STATISTICAL METHODS FOR TOLERABILITY ANALYSES

The trial will feature a two-stage minimax trial design (Simon 1989, A'hern, 2001) which tests for futility in a smaller sample of patients before proceeding with treatment of the full cohort. The accrual rate will be 1 patient/month in relapsed/refractory myeloid and B cell malignancies following allogeneic stem cell transplant to assess the safety and feasibility of pembrolizumab. The primary outcome is whether the patient remains DLT-free at the end of treatment. *A priori*, we expect 40% or fewer patients on an unsafe treatment would finish without experiencing a DLT, and at least 65% of patients would be DLT-free on a safe treatment. For $\alpha = 0.05$ and 80% power, we would need to observe

at least 5 DLT-free treatments out of a small sub-sample of 12 patients before we would consider evaluating pembrolizumab in the full sample of 26 patients. If at least 14 of the 26 patients respond remain DLT-free, we would have sufficient evidence to warrant further study of pembrolizumab in a future trial.

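### The stage-1 continue and halt limits do not agree, and the stated alpha of 0.05 with 80% power holds under neither reading (0.033 and 57.6% with the halt; 0.104 and 90.7% without it)

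*Combined protocol and SAP*

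**What the plan says.** Section 9.2.4.1 describes a two-stage minimax design with being DLT-free at the end of treatment as the primary outcome. Its planning rates are given as "40% or fewer patients on an unsafe treatment would finish without experiencing a DLT, and at least 65% of patients would be DLT-free". The second of these rates refers to a treatment regarded as safe. The section states an alpha of 0.05 with 80% power and sets this stage-1 requirement: "at least 5 DLT-free treatments out of a small sub-sample of 12 patients before we would consider evaluating pembrolizumab in the full sample". The whole trial has 26 patients, and the final rule is "If at least 14 of the 26 patients respond remain DLT-free, we would have sufficient evidence to warrant further study".

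Section 9.1.1 words the stage-1 rule as "If at least 5 of the first 12 patients complete pembrolizumab treatment without developing a DLT, we will open an expansion cohort". Sections 8.2 and 9.1.1 both add a condition to the expansion, namely "14 additional patients should DLT-associated stopping rule not be met in the first 12 patients". Section 9.1.1 then spells out that stopping rule: "if 5 or more of the first 12 enrolled patients develop a DLT, including grade 3-4 GHVD, then the study will be halted". Section 9.1.3 states the same limit: "if ≥ 5 of the first 12 enrolled patients develop a DLT, then the study will be permanently closed to accrual".

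Sections 9.1.1 and 9.1.3 also close the trial if each of the first 5 patients develops grade 3-4 GVHD.

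**The concern.** The number 5 is used in two opposite senses. As a count of DLT-free patients, 5 of 12 leaves room for 7 DLTs. As a count of DLTs, 5 of 12 leaves only 7 DLT-free, so continuing needs at least 8. If 5, 6 or 7 of the first 12 are DLT-free and the rest have DLTs, the limit in section 9.2.4.1 is met but sections 9.1.1 and 9.1.3 close the trial.

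The alpha and power in section 9.2.4.1 are given without mention of the halt. A halt that requires 8 of 12 is far stricter than one that requires 5 of 12, so the figures cannot describe a trial in which it operates. They may not describe the limits as printed either.

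This is the primary endpoint and the rule that decides whether 14 more patients are treated. Section 8.4.1 gives the evaluation after 12 patients to the principal investigator, so an unclear boundary would be resolved with the data in view.

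**Working it through.** **Inputs.** From section 9.2.4.1: n1 = 12, N = 26, unsafe DLT-free rate p0 = 0.40, safe rate p1 = 0.65, stage-1 limit 5 DLT-free, final limit 14 DLT-free, alpha 0.05, power 80%. From sections 9.1.1 and 9.1.3: halt at 5 or more DLTs of 12, and 14 patients in stage 2. Each patient is classed as DLT or DLT-free, following the binary outcome in section 9.2.4.1; this is relaxed in step 5.

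**Formula.** With stage-1 limit a and final limit r,

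P(success | p) = Σ over x = a to 12 of [ C(12,x) pˣ (1−p)¹²⁻ˣ × P(Bin(14,p) ≥ r − x) ].

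This is alpha at p = 0.40 and power at p = 0.65.

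**1. The plan's own figure, limits as printed and no halt (a = 5, r = 14).** Alpha = 0.1039 and power = 0.9073. The stated 0.05 and 80% are not reproduced.

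**2. Halt in force (a = 8, r = 14).**

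| DLT-free in stage 1 (x) | P(x), p = 0.65 | P(reach 14), p = 0.65 | P(x), p = 0.40 | P(reach 14), p = 0.40 |
|---|---|---|---|---|
| 8 | 0.2367 | 0.9757 | 0.0420 | 0.5142 |
| 9 | 0.1954 | 0.9940 | 0.0125 | 0.7207 |
| 10 | 0.1089 | 0.9989 | 0.0025 | 0.8757 |
| 11 | 0.0367 | 0.9999 | 0.0003 | 0.9602 |
| 12 | 0.0057 | 1.0000 | 0.0000 | 0.9919 |

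Summing the products gives power 0.5763 and alpha 0.0331. P(at least 8 of 12 | 0.65) = 0.5833, so no final cut-off can raise power above 58.3%. The chance of stopping at stage 1 at the safe rate is 1 − 0.5833 = 0.4167.

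**3. Limits that do match the stated figures.** An exhaustive search at 0.40 versus 0.65, with alpha at most 0.05 and power at least 0.80, gives a smallest N of 26. Among designs of that size, the one with the lowest expected sample size at p0 (16.7) has n1 = 12, stops at 5 or fewer of 12 and fails at 14 or fewer of 26. Continuing therefore needs at least 6 of 12 and success at least 15 of 26: alpha 0.0469, power 0.8086. The plan's four integers (12, 26, 5, 14) are exactly these, but 5 and 14 are printed as minimum counts for going on rather than as the highest counts for stopping. That origin is an inference; the mismatch in error rates is arithmetic.

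**4. How often the two stage-1 limits disagree.** P(5, 6 or 7 DLT-free of 12):

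- p = 0.65: 0.0591 + 0.1281 + 0.2039 = 0.391
- p = 0.50: 0.1934 + 0.2256 + 0.1934 = 0.612
- p = 0.40: 0.2270 + 0.1766 + 0.1009 = 0.505

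**5. Patients who are neither.** Sections 8.2 and 9.1.1 count patients who complete treatment without a DLT. Someone who leaves early, for example at progression, may be neither a completer nor a DLT. The documents give no rate, so the following is an assumption. The DLT-free rate is held at 0.65 or 0.40, a share q is moved out of the DLT group, and the trial continues with at most 4 DLTs and at least 5 DLT-free; success is at least 14 of 26.

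| q | Power | Alpha | P(halt) at the 0.65 rate |
|---|---|---|---|
| 0% | 0.576 | 0.033 | 0.417 |
| 5% | 0.702 | 0.046 | 0.276 |
| 10% | 0.799 | 0.060 | 0.158 |
| 15% | 0.862 | 0.072 | 0.073 |
| 20% | 0.894 | 0.083 | 0.024 |
| 30% | 0.907 | 0.097 | 0.0002 |

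No row has both alpha at or below 0.05 and power at or above 80%.

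**6. The rule on the first 5 patients.** Approximated as 5 DLTs in the first 5, it changes step 1 to 0.1033 and 0.905 and leaves step 2 unchanged.

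**The case against.** The strongest reply is that the passages can be read together. Section 9.2.4.1 states what must be seen before the full sample is considered, which is a necessary condition and not a promise to expand. Sections 8.2 and 9.1.1 make expansion conditional on the stopping rule. Apply both rules and the halt governs. That reading is reasonable. But under two-way classing the limit of 5 DLT-free then never decides anything, and section 9.2.4.1 still gives 80% power for a design that has 57.6%.

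Second, alpha of 0.05 is a ceiling, so 0.033 does not breach it. This is right: with the halt and two-way classing the failure is in power alone.

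Third, the 57.6% and 41.7% depend on every patient being either a DLT or DLT-free. With many early leavers the picture turns round: power passes 80% and alpha is too high. This also stands, so it cannot be said generally that the halt costs only power. It does not rescue the stated pair, which fails across the whole range tried.

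Fourth, section 9.1.3 runs the interim once 12 patients have had at least one dose. With a 90-day DLT window (section 2.1) and one patient a month, the latest patients would be incompletely observed. If only 9 or 10 were fully observed (an assumption), P(5 or more DLTs) at a 35% DLT rate is 17% or 25%, not 41.7%. So the 41.7% supposes complete follow-up of all 12.

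Finally, this is a pilot and the off-by-one may be a slip of transcription. Even so, the printed cut-offs are the ones that would be applied.

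**Conclusion.** The concern holds. The plan contains two different stage-1 limits, and its alpha and power describe neither. If the halt governs, every patient is classed as DLT or DLT-free and all 12 are fully followed, power is 57.6% rather than 80%, with alpha 0.033. If the printed two-stage limits apply without the halt, alpha is 0.104 rather than 0.05, with power 90.7%. If some patients are neither, the halt gives values between these, and the stated pair is still not met. The point must be fixed because it concerns the primary decision rule and the power claimed for it.

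**What to change.** - Reconcile sections 8.2, 9.1.1, 9.1.3 and 9.2.4.1 to a single stage-1 boundary, written identically in each place both as a number of DLTs and as a number of DLT-free patients. Which boundary applies is for the sponsor to settle.
- State how a patient who leaves treatment early without a DLT is counted at stage 1 and in the final count.
- Replace the stated alpha and power with the exact values for the stage-1 and final cut-offs actually used. If the 5-DLT halt is kept with 14 of 26, those are about 3% and 58% under two-way classing. If the two-stage boundary is kept without the halt, either restate the error rates for the printed limits or bring the limits into line with 0.05 and 80%.

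The cost is protocol and SAP wording and a short recalculation, with no extra patients. If the halt is kept, the power to be reported is less favourable than the one now stated, unless enough patients prove to be neither DLT nor DLT-free.

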A DLT is defined as the development of grade 3 or 4 acute GVHD (defined by the Gluckensberg scale), graft rejection, the development of any unexpected grade > 2 toxicity felt to be related to pembrolizumab, or the development of > grade 2 dysfunction of a vital organ felt to be secondary to an immune-related adverse event within 90 days following the initiation of pembrolizumab treatment. For immune-related adverse events that do not meet criteria for a DLT, but do meet criteria for a treatment-limiting toxicity (TLT), for example grade 2 acute GVHD, pembrolizumab will be held until the toxicity has

decreased to \leq grade 1. It will be permanently discontinued if delayed for >12 weeks. For patients who develop GVHD or an immune-related adverse event while on pembrolizumab, corticosteroid therapy and potentially other immunomodulatory agents will be initiated.

If the safety and feasibility of pembrolizumab is confirmed in this patient cohort, a phase II expansion cohort may be considered, particularly for disease subtypes where objective responses have been observed.

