6.10 CRITERIA FOR EARLY TRIAL TERMINATION

Early trial termination will be the result of the criteria specified below:

1. Quality or quantity of data recording is inaccurate or incomplete
2. Poor adherence to the protocol and regulatory requirements
3. Plans to modify or discontinue the development of the study drug
4. Early stopping rule(s) are met

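### The only stated time for acting on 5 DLTs in the first 12 patients is after patient 12 is dosed, so accrual can run on once the stage-1 stop is certain

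*Combined protocol and SAP*

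**What the plan says.** Section 9.1.1 sets the stage-1 stopping boundary: "if 5 or more of the first 12 enrolled patients develop a DLT, including grade 3-4 GHVD, then the study will be halted". It attaches no time to the halt. Section 6.10 lists "Early stopping rule(s) are met" as a ground for ending the trial early, also without a time.

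Section 9.1.3 supplies the only time: "After the first 12 patients have been enrolled and have received at least 1 dose of pembrolizumab, an interim safety analysis will be performed". Fewer than 5 DLTs opens a 14-patient expansion. Otherwise, "if ≥ 5 of the first 12 enrolled patients develop a DLT, then the study will be permanently closed to accrual".

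Both sections add a narrower rule. In the words of 9.1.3, "if severe GVHD (grade 3-4) develops in each of the first 5 patients treated on the study, it will be permanently closed to accrual". Section 9.1.1 limits this rule to the first 90 days of treatment, which makes each such event a DLT.

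Section 9.2.4.1 describes a two-stage design that "tests for futility in a smaller sample of patients before proceeding with treatment of the full cohort". Section 8.4.1 says that the trial will be "evaluated by the principal investigator after the first 12 patients are enrolled to assess if the trial should be continued"; it mentions neither the 5-DLT boundary nor dosing. Section 2.1 counts a DLT if it arises "within 90 days following the initiation of pembrolizumab treatment". Planned accrual is one patient per month (9.1.1, 9.2.4.1).

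**The concern.** Once five of the first 12 patients have had a DLT, later patients cannot undo the boundary, and stage 1 must end in closure. If the boundary is read only at the 9.1.3 analysis, nothing written stops enrolment between the fifth DLT and patient 12. Patients would be newly exposed in a trial whose primary objective is tolerability, after its own safety criterion had been met.

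The five-of-five rule bears on how to read the text. Five of the first 5 are already five of the first 12, so that rule does nothing if the 5-of-12 boundary acts continuously. Its presence suggests a boundary that waits for patient 12. It would then be the only numeric cohort rule before patient 12, and it counts GVHD alone. The DLT definition also covers graft rejection, unexpected toxicity above grade 2 related to the drug, and immune-related organ dysfunction above grade 2.

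**Working it through.** **Inputs.** The DLT rates are 1 - 0.40 = 60% (unsafe) and 1 - 0.65 = 35% (safe), from 9.2.4.1. The DLT window is 90 days (2.1) and accrual is one patient per month (9.1.1). The documents give no onset distribution, so three are assumed: uniform over days 0-30, days 0-90 and days 60-90. Patient *i* is first dosed on day 30.4 × (*i* - 1), so patient 12 starts on day 334.4. Progression and withdrawal are ignored. The 5-DLT boundary is taken as written.

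**Step 1: chance of reaching the boundary at all.** P(X ≥ 5), X ~ Bin(12, p), is 0.943 at 60% and 0.417 at 35%.

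**Step 2: exact ceiling.** For the fifth DLT to precede patient 12's first dose, at least five must fall among patients 1-11. P(X ≥ 5), X ~ Bin(11, p), is 0.901 at 60% and 0.332 at 35%. With onset inside 30 days and 30.4-day spacing, every such DLT precedes patient 12, so the ceiling is attained.

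**Step 3: simulation, 400,000 trials per setting.** The last two columns are means over trials in which the fifth DLT precedes patient 12's first dose.

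| DLT rate | Onset (days) | P(fifth DLT before patient 12 is dosed) | Patients first dosed after it | DLTs among them |
|---|---|---|---|---|
| 60% | 0-30 | 0.900 | 4.21 | 2.52 |
| 60% | 0-90 | 0.827 | 3.53 | 2.12 |
| 60% | 60-90 | 0.736 | 2.83 | 1.70 |
| 35% | 0-30 | 0.331 | 2.85 | 1.00 |
| 35% | 0-90 | 0.251 | 2.52 | 0.88 |
| 35% | 60-90 | 0.173 | 2.12 | 0.74 |

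The 0-30 rows agree with step 2. Averaged over all trials, the extra exposure at 60% runs from 0.736 × 2.83 = 2.1 to 0.900 × 4.21 = 3.8 patients. At 35% it runs from 0.173 × 2.12 = 0.4 to 0.331 × 2.85 = 0.9.

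If confirming a DLT takes 14 days, the 60% figures become 0.871, 0.786 and 0.673 for the probability, 3.89, 3.23 and 2.59 patients, and 2.34, 1.94 and 1.56 DLTs.

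**Step 4: does the five-of-five rule fill the gap?** Even if every DLT were grade 3-4 GVHD, it fires with probability 0.60^5 = 0.078 or 0.35^5 = 0.005.

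**Step 5 (separate): a fifth DLT after the analysis.** When patient 12 is first dosed, patients 10, 11 and 12 have 60.8, 30.4 and 0 days of follow-up, so their windows are open. The chance of fewer than 5 DLTs at the analysis but 5 or more once all windows close is:

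| Analysis date | 60% | 35% |
|---|---|---|
| Patient 12's first dose | 4-21% | 9-24% |
| 30 days later | 0-11% | 0-17% |
| 90 days later | 0% | 0% |

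**Step 6: success probabilities.** Requiring at least 8 of 12 DLT-free (fewer than 5 DLTs) and then 14 of 26, the sum over x = 8 to 12 of Bin(x; 12, q) × P(Y ≥ 14 - x), Y ~ Bin(14, q), is 0.033 at q = 0.40 and 0.576 at q = 0.65. With only the go rule of 5 of 12 DLT-free, the figures are 0.104 and 0.907. An analysis 90 days after patient 12's first dose gives the same 0.033 and 0.576 as a boundary that acts continuously.

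**The case against.** Section 9.1.1 is headed as a summary and is silent on timing, so it does not contradict 9.1.3. The plan also has general safeguards. Under 8.2 the rate of entry depends on the safety profile, and under 8.2.3.3 the principal investigator monitors aggregate safety data. Serious events and events of clinical interest must be reported within 24 hours (8.2.3.1, 8.2.3.2), and 11.3 refers to a cancer-center monitoring plan that is not among the documents. An attentive investigator might well stop at the fifth DLT. All of this stands, but none of that text sets a number, and a written boundary should not depend on discretion to act when it is met.

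Three stronger readings are tempting, and the documents do not support them.

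- A reader might infer that the plan gives conflicting action times. It gives one, in 9.1.3. Section 8.4.1 supports only an evaluation by the principal investigator after 12 are enrolled.
- A reader might treat late DLTs (step 5) as a difference between continuous and single-look monitoring. They arise from incomplete 90-day follow-up and vanish if the analysis waits 90 days.
- A reader might set 0.576 against the stated 80% power and call it a cost of timing. Step 6 shows that the loss comes from the 5-DLT stop overriding the rule that 5 of 12 DLT-free suffices, which is a separate matter.

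**Conclusion.** The point holds as a minor gap in a safety rule. The only stated time for acting on the boundary comes after patient 12 has been dosed, and the text leaves open whether the halt in 9.1.1 can act sooner. Under the stated timing, enrolment past a stage-1 stop that is already certain is the usual outcome at the unsafe rate and a minority outcome at the safe rate, where it costs about one additional DLT or fewer in the trials affected. These sizes rest on the planned accrual rate, the assumed onset patterns and no loss to progression or withdrawal. A 14-day confirmation delay reduces them only modestly.

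Late DLTs are secondary. The frequency runs from 0 to 24% depending on analysis date, onset and DLT rate, and whether such an event closes the expansion is the sponsor's choice.

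**What to change.** In 9.1.1 and 9.1.3 write: *If a fifth DLT among the first 12 patients is confirmed before the interim analysis, accrual is permanently closed on that day without waiting for the analysis.* Drop the five-of-five GVHD rule, which this sentence contains given the 90-day limit in 9.1.1.

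The cost is wording only. The sentence is limited to DLTs confirmed before the analysis, so the boundary has already been met whenever it acts and no stage-1 decision changes. The only loss is data on the patients who are not enrolled.

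Separately, state in 9.1.3 whether a fifth DLT that arises after the analysis, but within its 90-day window, closes the expansion. Alternatively, schedule the analysis 90 days after patient 12's first dose, which removes the question at the price of a later expansion decision.

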The choice of the 200 mg Q3W as an appropriate dose for the switch to fixed dosing is based on simulations performed using the population PK model of pembrolizumab showing that the fixed dose of 200 mg every 3 weeks will provide exposures that 1) are optimally consistent with those obtained with the 2 mg/kg dose every 3 weeks, 2) will maintain individual patient exposures in the exposure range established in melanoma as associated with maximal efficacy response and 3) will maintain individual patients exposure in the exposure range established in melanoma that are well tolerated and safe.

A fixed dose regimen will simplify the dosing regimen to be more convenient for physicians and to reduce potential for dosing errors. A fixed dosing scheme will also reduce complexity in the logistical chain at treatment facilities and reduce wastage. Therefore 200mg pembrolizumab Q3W will be used in the current study.

5.3 RATIONALE FOR TOLERABILITY ENDPOINTS.

The primary endpoint of this trial is to determine whether pembrolizumab administration is safe and tolerable in patients with relapsed AML, MDS, and mature B cell lymphomas following alloSCT. The safety analysis will be based on subjects who experience toxicities following treatment with pembrolizumab as defined by CTCAE criteria. Safety will be assessed by quantifying and grading the toxicities experienced by subjects who have received pembrolizumab, including serious adverse events (SAEs) and events of clinical interest (ECIs). Safety will be assessed by reported adverse events using CTCAE, version 4.0. The attribution to drug, timing of onset, event duration, event resolution, and any concomitant medications administered will be recorded. AEs will be analyzed, including but not limited to all AEs, SAEs, fatal AEs, and laboratory changes. Further, the occurrence of a grade 2 or higher immune-related AE will be collected and designated as an immune-related event of clinical interest (irAE) as well as veno-occlusive disease (VOD) and steroid-requiring febrile syndrome. Special attention will be paid in this patient population, to the development and severity of acute GVHD, which will be appropriately staged and graded according to accepted criteria (see Appendix, Section 13.6).

Given that a standard, phase I dose-escalation approach is not warranted given the discussion in Section 5.2, the investigators feel it is reasonable to perform a pilot study to

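### Section 9.1.1 defines a maximally tolerated dose that a one-dose trial cannot derive, and its 1-in-6 DLT limit disagrees with the 14-of-26 success rule on how the tolerability result would be reported.

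*Combined protocol and SAP*

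**What the plan says.** Section 9.1.1 (Safety analyses) holds two numerical statements about DLTs.

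- An MTD definition: "the maximally tolerated dose will be defined a less or equal than 1 in 6 patients with DLTs". The sentence after it makes every patient who received any study drug evaluable for toxicity.
- A success rule: "If at least 14 of the 26 patients remain DLT-free, we would have sufficient evidence to warrant further study of pembrolizumab in a future trial". Section 9.2.4.1 repeats the cut-off ("If at least 14 of the 26 patients respond remain DLT-free") and sets the design rates: 40% DLT-free or fewer is unsafe, at least 65% DLT-free is safe.

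For stage 1, Section 9.1.3 opens the expansion cohort "If < 5 of the first 12 patients develop a DLT (including grade 3-4 acute GVHD) following pembrolizumab treatment" and closes accrual at 5 or more. Section 9.2.4.1 asks instead for "at least 5 DLT-free treatments out of a small sub-sample of 12 patients". Section 9.1.1 contains both versions.

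On dose, Sections 2.1 and 6.2.1.1 give every subject 200 mg every three weeks. Section 5.3 explains the pilot design by saying "Given that a standard, phase I dose-escalation approach is not warranted given the discussion in Section 5.2". Section 8.2 nevertheless begins: "The rate of subject entry and expansion will depend upon assessment of the safety profile of patients entered at the previous dose level".

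**The concern.** An MTD is chosen from several doses. This trial has one dose, no escalation and no cohort of six, so the definition in Section 9.1.1 has nothing to act on. Section 8.2 likewise refers to an earlier dose level that does not exist. Both sentences read like text from an escalation design.

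The 1-in-6 figure is also far stricter than the criterion the trial uses. Tolerability is the primary objective, and the hypothesis in Section 3.1 speaks of an acceptable incidence of immune-related events without giving a number. A reader of the final report would therefore look to Section 9 for the standard and find two. The same DLT count could be reported as enough to warrant further study and as above the protocol's own MTD limit. The choice of which to stress could be made after the count is known.

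**Working it through.** **Inputs.** MTD limit 1/6 (9.1.1). Success at 14 or more DLT-free of 26 (9.1.1, 9.2.4.1). Stage 1 of 12 patients, with a halt at 5 or more DLTs (9.1.1, 9.1.3) or continuation at 5 or more DLT-free (9.1.1, 9.2.4.1). Design rates 40% and 65% DLT-free, alpha 0.05, power 80% (9.2.4.1).

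**The plan's own design figure.** An exact minimax search at these rates returns 12 and 26 patients, as the plan states. Its cut-offs are continue at 6 or more and succeed at 15 or more DLT-free (alpha 0.047, power 0.809). The rule as written, 5 and 14, gives alpha 0.104 and power 0.907. That is a separate matter. It is noted here because the comparison below uses the written cut-off of 14.

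**Limits side by side.**

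- Success rule: 26 − 14 = 12 DLTs allowed; 12/26 = 46.2%.
- MTD sentence, read as a proportion of all treated patients: 26/6 = 4.33, so at most 4 DLTs; 4/26 = 15.4%.
- Safe rate in 9.2.4.1: 100% − 65% = 35% DLTs, against 16.7% for 1 in 6.
- Zone where the two disagree: 5 to 12 DLTs of 26 (19.2% to 46.2%). With a cut-off of 15 it would be 5 to 11, so the conflict does not depend on that choice.

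**How likely is that zone?** Let X1 be the DLTs in the first 12 patients and X2 those in the next 14, independent binomial variables with common rate p. With the halt,

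P(both verdicts) = P(X1 ≤ 4 and 5 ≤ X1 + X2 ≤ 12).

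A total of 4 or fewer DLTs can never trigger the halt, so this equals P(pass) − P(X1 + X2 ≤ 4). Without the halt, X1 ≤ 4 is replaced by X1 ≤ 7.

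| True DLT rate | P(at most 4 of 26) | P(pass), with halt | P(pass with 5–12 DLTs), with halt | Same, without halt |
|---|---|---|---|---|
| 10% | 0.8882 | 0.9957 | 0.1075 | 0.1118 |
| 15% | 0.6505 | 0.9761 | 0.3256 | 0.3494 |
| 16.7% | 0.5584 | 0.9636 | 0.4053 | 0.4414 |
| 25% | 0.1844 | 0.8418 | 0.6575 | 0.8085 |
| 35% | 0.0242 | 0.5763 | 0.5521 | 0.8831 |

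Differences between columns may be off by one in the last digit from rounding. The documents give the 35% rate (safe limit) and 1 in 6; the 10%, 15% and 25% rates are assumed, to show the range.

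With the halt, the probability falls from 25% to 35% because more trials stop at stage 1. Among trials that pass at 35%, 0.5521/0.5763 = 96% would have more than 4 DLTs.

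**The case against.** The strongest reply is that the MTD sentence does nothing. The primary objective (3.1), the endpoint rationale (5.3), the interim rule (9.1.3) and the tolerability methods (9.2.4.1) never mention an MTD. Section 9.1 calls itself a brief summary and sends the reader to the full SAP. It misnumbers that section as 8.2, but the contents list shows it is 9.2, and 9.2.4.1 carries only the two-stage rule. This stands. It is not a precedence clause, but it tells a statistician which text to follow. A reader might infer that the trial's primary decision, or its conduct, turns on which sentence is applied. The documents do not support that.

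Second, a reader might infer from the 2.4% at a 35% DLT rate that a safe treatment would almost always fail the 1-in-6 limit. That is true only near the edge of the safe range. Section 9.2.4.1 calls any DLT-free rate of 65% or more safe, and at DLT rates of 10% and 15% the limit is met with probability 89% and 65%.

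Third, the sentence gives no denominator. The line on evaluability that follows it makes all treated patients a natural reading, but it remains a reading. Scaled to stage 1, 1 in 6 would be 2 of 12, and a reader might infer a further conflict at 3 or 4 DLTs. Nothing says an MTD is judged at the interim, so that inference is not supported.

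Fourth, the plan's term for a pass is that further study is warranted, not that the dose is tolerable. The rule does sit under the tolerability methods, so the link to the primary objective is fair.

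**Conclusion.** The point holds as an inconsistency in operative text. No MTD can be derived from one fixed dose. On the all-treated reading, the 1-in-6 limit contradicts the success rule for every result from 5 to 12 DLTs of 26. With the halt at 5 of 12, such a result has probability 11%, 33%, 66% and 55% at true DLT rates of 10%, 15%, 25% and 35%. These figures assume independent patients with a common DLT rate, 26 evaluable patients if the trial expands, and the written cut-off of 14. They count patients who leave early without a DLT as DLT-free; counting them as failures would lower the chance of a pass but leave 12 as the most DLTs a pass can contain.

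The consequence is confined to how the primary tolerability result is interpreted and reported. It should be corrected, but it does not change enrolment, stopping or the success decision.

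**What to change.** Reconcile Sections 9.1.1 and 9.2.4.1 so that one pre-stated DLT criterion decides tolerability. Remove the MTD claim from 9.1.1, since one dose cannot yield an MTD, and remove the sentence in 8.2 that ties entry and expansion to an earlier dose level. If the 1-in-6 limit is meant to have a role, state its denominator, when it is assessed and what it decides, and say how it relates to the 14-of-26 rule. Which DLT limit is appropriate is for the sponsor and investigators; this review does not propose one.

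The disagreement between the stage-1 rules (continue at 5 or more DLT-free, halt at 5 or more DLTs) needs its own correction. It accounts for the gap between the last two columns of the table.

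The cost is a wording change to the protocol and SAP, with no added patients, visits or procedures.
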